5. STUDY DESIGN

5.1 DESCRIPTION

This study has been designed as a longitudinal, double blind, crossover study. Specifically, a split mouth design will be implemented to investigate if there is a significant difference in pain perception between administering buffered local anesthesia versus conventional local anesthesia in a pediatric patient. We will also investigate time of onset of local anesthesia and compare buffered to non-buffered solutions. Patients will be treated by a single pediatric dental resident while being overseen by a board-certified attending pediatric dentist at Geisinger Medical Center (GMC). This study will be implemented upon receiving Institutional Review Board (IRB) approval.

The population of interest includes healthy children aged 4-17yo. Children selected for this study will be assessed using the American Society of Anesthesiologists (ASA) physical status classification system. In an effort to control for confounding variables, only healthy children classified as ASA I or ASA II will be included in this study. Children selected for this study will have been determined to require treatment on two or more occasions on opposite sides of the mouth. If a patient has multiple issues on each side of the mouth, the patient may be asked to participate in the study procedures for a second time. This could result in seeing the patient for 4 separate visits. Patients will not be excluded if they develop localized infection requiring treatment without systemic antibiotics, however, they will only remain in the study if both sides requiring treatment are either free of infection or if both sides have a localized pain or infection requiring treatment without systemic antibiotics. Patients must have no allergy to lidocaine or

history of adverse reactions to epinephrine, no history of hyperthyroidism, and no significant cardiovascular disease per recommendations for administration of local anesthetic according to the American Academy of Pediatric Dentistry (AAPD).¹² Buffered lidocaine has been approved for use in patients for medical and dental procedures. There is no additional cost to the patient for receiving buffered versus non-buffered solution.

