On the day of the procedure, the side of the mouth that is treated first will be based on the patient's chief complaint. If the patient does not have a chief complaint, the side of the mouth that is treated first will be the side of the mouth with more significant dental caries. The attending pediatric dentist will flip a coin to determine if the patient will receive the buffered or conventional local anesthetic solution during the first visit, with the "heads" side being assigned to the buffered solution, and the "tails" side assigned to the non-buffered solution. At the patient's second visit, the alternative local anesthetic solution will be used, and the other side of the mouth will be treated.

IRB NUMBER: 2019-0408 IRB Approved: 12/12/2019

[figure not shown]
The attending pediatric dentist will have access to a protected Excel spreadsheet containing information related to each patient including: patient name, medical record number (MRN), the patient's number assignment (as discussed above), date of the first and second visit, which local anesthetic solution was administered at each visit, the local anesthesia technique used (infiltration vs IANB), which arch (maxilla vs mandible) was treated, and which side of the mouth was treated. This document will be locked and the operator will not have access to this spreadsheet in order to preserve the double-blind nature of this study.

Vasoconstrictors, like epinephrine, become unstable with an increase in pH⁹. Local anesthetic solutions with a vasoconstrictor are traditionally prepared as an acidic solution to extend shelf life⁹. Buffering our local anesthesia containing epinephrine will reduce the stability of solution from approximately 8-12 months to a shelf life of only seven days¹³. Although the solution has been said to be stable for a week, to ensure stability of the solution, and control for confounding variables, the buffered solutions will be mixed immediately before administering the solution. Other study designs have used this approach to mix the solution immediately before administration^{1,9}.

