During the appointment requiring the buffered local anesthesia solution, the attending will prepare 1:10 dilution of sodium bicarbonate to local anesthesia. A 1.7mL vial of commercially available 2% lidocaine hydrochloric acid with 1:100,000 epinephrine (Lignospan standard, Septodont Lancaster, Pennsylvania (PA) will be used. The cartridge of lidocaine and the bottle of sodium bicarbonate will be wiped with an alcohol pad. 0.17mL of 8.4 percent sodium bicarbonate will be added into the local anesthesia cartridge to make the final preparation. The pH of traditional 2% lidocaine with 1:100,000 epinephrine is typically acidic to prolong shelf life; the pH is approximately 4.5.8 The buffered solution will be tested using a pH tester (Water Quality Test Meter Pancellent TDS PH EC Temperature 4 in 1 Kit, Pancellent) to evaluate the pH range of this preparation, and to verify a value above 5.5.

The attending will bring the cartridge of anesthetic to the operatory and load the syringe. The operator and patient will remain blinded to the type of local anesthesia that is used. For this study, if the patient requires treatment of the lower posterior teeth, a IANB will be the injection technique of choice. If the patient requires treatment in the posterior maxilla, an infiltration will be the injection technique of choice. After a period of no less than one week, the patient will return for a second visit. At the second visit, the solution of local anesthesia will be alternated, and the opposite side of the mouth will be treated.

Prior to initiation of treatment, patients will rate their pain using the Wong-Baker FACES Pain Scale in order to establish a baseline and to help eliminate confounding variables. Also before treatment, a tooth that will be anesthetized will be probed with a periodontal probe to establish a baseline perception of this sensation without local anesthesia. Upon probing without local anesthesia, the patient will ask if they feel a "pinch," in order to

establish this baseline. When asked if they feel a pinch, patients will respond with a "yes" or "no" answer, which will be recorded.

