5.5 STATISTICS

5.5.1 Statistical Analysis Plan

Data will be analyzed using t-tests to examine treatment differences. Given patients will be treated with both methods, they will act as their own controls and paired t-tests will be utilized. If covariates are identified (e.g., patients' baseline pain perception), Repeated measure ANOVAs will be utilized with patients as within-subject variable and the patient experience as the outcome.

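### The SAP leaves out visit order, leaves the baseline-pain adjustment open and misnames the within-subject factor: a precision and prespecification gap, not a bias

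*Combined protocol and SAP*

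**What the plan says.** Section 5.5.1 (Statistical Analysis Plan) says of the patients that "they will act as their own controls and paired t-tests will be utilized". It then adds a conditional analysis, which begins "If covariates are identified (e.g., patients' baseline pain perception" and continues: "Repeated measure ANOVAs will be utilized with patients as within-subject variable and the patient experience as the outcome". Nothing in Section 5.5 mentions visit, period, order or sequence.

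Three parts of Section 5.1 (Description) bear on this:

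- **Baseline pain.** Before treatment, "patients will rate their pain using the Wong-Baker FACES Pain Scale in order to establish a baseline and to help eliminate confounding variables". The text does not say expressly that this is done at every visit.
- **Side treated first.** "the side of the mouth that is treated first will be based on the patient's chief complaint"; failing a chief complaint, "the side of the mouth that is treated first will be the side of the mouth with more significant dental caries".
- **Order of solutions.** "The attending pediatric dentist will flip a coin to determine if the patient will receive the buffered or conventional local anesthetic solution" at the first visit. The other solution, on the other side, follows at the second visit.

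Section 5.1 also lets a child with several problems on each side go through the procedures again, for up to four visits.

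**The concern.** There are three gaps.

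1. **Factor name.** A repeated-measures ANOVA with patient as the within-subject variable does not describe the intended contrast.
2. **Baseline pain.** It is collected to deal with confounding, but the SAP does not say when it enters or in what form. The form matters. One value per child, entered as a main effect, cannot change a within-child contrast; a value for each visit can. If the choice is left until the data are seen, the analyst can pick between an adjusted and an unadjusted result.
3. **Visit order.** The side with the complaint or the worse decay comes first, so the two visits may differ systematically in pain. An unmodelled visit effect adds variance to the buffered-minus-conventional difference. Because the coin flip is unrestricted, the two orders may also be unequal in number.

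At stake are some power and a fixed primary analysis. The validity of the planned test is not in question.

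**Working it through.** **Inputs.** From Section 5.5.2: d = 0.50, 90% power, 44 evaluable, 20% attrition, 55 enrolled. Assumed, because the documents give no value: two-sided 5% significance; d standardised by the SD of the within-patient difference; the visit effect π (mean visit-1 minus visit-2 score, in units of that SD); and r, the correlation between the within-patient baseline difference and the within-patient outcome difference. One pair per child throughout.

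**The plan's own figure.** Paired t-test, noncentral t with 43 df and noncentrality 0.50 × √44 = 3.317: power 90.0%. Enrolment is 44 / 0.80 = 55. Both figures reproduce, which supports the first two assumptions.

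**Balance of the coin flip.** With 44 fair flips, a 28:16 split or worse in either direction has probability 0.096. At 28:16 an unmodelled visit effect of 0.3 SD shifts the estimate by 0.3 × (28 − 16)/44 = 0.08 SD. The direction is random, so over repeated randomisation this is noise, not bias.

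**Visit order.** Model: D = δ + π·o + error. D is buffered minus conventional, o is +1 or −1 for the order of solutions, and δ (the intercept) is the treatment effect.

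- Without the order term, the SD of D becomes √(1 + π²), so the effective d is 0.50/√(1 + π²). At π = 0.3 this is 0.479; at π = 0.5 it is 0.447.
- With the order term, there are 42 df and the effective n is 44 × [1 − ((a − b)/44)²] for an a:b split. Averaged over the coin flip, power is 89.3% whatever π is. At 28:16 the effective n is 44 × 0.926 = 40.7.

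| π (assumed) | Unadjusted | Order in model | Change |
|---|---|---|---|
| 0 | 90.0% | 89.3% | −0.7 |
| 0.1 | 89.7% | 89.3% | −0.4 |
| 0.2 | 88.9% | 89.3% | +0.4 |
| 0.3 | 87.4% | 89.3% | +1.9 |
| 0.5 | 82.6% | 89.3% | +6.7 |

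Simulation with 100,000 trials per cell agrees to within about 0.2 point.

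**Baseline difference.** Simulated power with no visit effect:

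| r (assumed) | Unadjusted | Baseline difference and order |
|---|---|---|
| 0 | 90.0% | 88.5% |
| 0.20 | 90.1% | 89.7% |
| 0.25 | 90.0% | 90.3% |
| 0.30 | 90.1% | 91.2% |
| 0.50 | 90.2% | 95.4% |

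Break-even for the two terms together is at r of about 0.20 to 0.25. In one simulated data set, a single baseline value per child left the standard error of the contrast at 0.198; the visit-specific value brought it to 0.188 (sample r = 0.36).

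**Open choice of model.** Each fixed model has a type I error of about 5%. If the more favourable of the unadjusted and baseline-adjusted results were always reported, type I error would be about 5.6% at r = 0, 6.3% at r = 0.3 and 7.3% at r = 0.5. The simulations together span about 5.6 to 7.4%.

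**The case against.** The strongest reply is that no harm to the planned analysis is shown. The paired t-test is valid, the sample size is right, and the factor name is a slip whose meaning is clear from the sentence before it. All of that stands.

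Second, any gain rests on quantities that the documents do not give, and the design limits them. Inclusion criterion 1 (Section 5.2.2) keeps both sides in the same arch with similar teeth or regions. Section 5.1 says of patients who develop a localised infection that "they will only remain in the study if both sides requiring treatment are either free of infection" or both are affected alike. These rules may keep the visit effect small and the baselines similar, though they do not remove a difference built into which side goes first. At a visit effect of 0.1 SD the order term does not help.

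Third, a reader might infer that the baseline-adjusted regression should become the primary analysis. The documents do not support that. Baseline FACES is pain before treatment and the outcome is pain on injection; no correlation between their within-child differences is given. With six faces, tied baselines are likely. In a six-face simulation with a latent link of 0.5, full-model power fell from 93.8% to 90.6% as the share of tied baselines rose from 39% to 82%, against about 90% unadjusted. Below r of about 0.2 the model loses power. The gain from the order term is a separate matter: it depends on the visit effect and not on r.

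Fourth, baseline FACES may already be meant for each visit, since Section 5.1 places it within the appointment procedure. That calls for a clarification only.

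**Conclusion.** The three textual gaps are certain: the factor is misnamed, the baseline adjustment has neither trigger nor form, and visit order is absent although the visits differ by design. The consequence is modest. For visit order it is a cost of about 0.7 point of power if there is no visit effect, against a gain of about 2 to 7 points for an assumed effect of 0.3 to 0.5 SD. For the open covariate clause it is a worst-case type I error of about 5.6 to 7.4%. That is an upper bound on what the wording permits, not a forecast of how the analysis will be done.

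A reader might infer from the non-random choice of first side that the treatment comparison is biased, or that the trial is underpowered. Neither follows. The coin flip makes the order of solutions independent of which side goes first, and 44, 55 and 90% reproduce. The power figures assume a two-sided 5% test, normal differences and one pair per child.

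**What to change.** Amend Section 5.5.1 before unblinding.

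(a) **Primary analysis.** Regress the within-patient buffered-minus-conventional difference on visit order coded −1/+1, with the intercept as the treatment effect. Keep the unadjusted paired t-test as a sensitivity analysis. Cost: one degree of freedom and about 0.7 point of power if the visits do not differ. Visit dates and the solution given are already in the attending dentist's locked spreadsheet.

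(b) **Baseline pain.** Replace the conditional covariate clause with one named secondary analysis that adds the within-patient difference in visit-specific baseline FACES. State that baseline FACES is rated at each visit, and give it its own entry in the outcome spreadsheet, which does not list it separately. As a secondary analysis it costs the primary comparison no power.

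(c) **Wording and repeat participation.** Name solution as the within-subject factor and patient as the block. State how two pairs from one child enter the analysis, for example with patient as a random effect.

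The cost is SAP text and one data field; no clinical procedure changes.

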5.5.2 Statistical Power and Sample Size Considerations

Approximately 55 patients will be included in the study. Based on a medium effect size (Cohen's d=.50) observed in similar research (Kurien, Goswami, & Singh, 2018), a sample of 55 patients with data from two timepoints will provide 90% power and allow for a 20% (n=11) rate of attrition. For analyses examining paired differences between lidocaine treatments, a sample of 44 will provide adequate power.

6. DATA MANAGEMENT

Only approved study staff will have access to data collected for this research. Electronic data will be stored on Geisinger's secure network. Any hard copy data will be secured in a locked office or cabinet. Only research team members can access the data files. Records of data generated in the course of the study shall be retained for at least 6 years after the study ends and could be used for future research studies submitted and approved by the IRB. To protect the double-blind design, the randomization excel sheet will only be available to the study physicians until the end of the study.

Face	No particular expression or smile	Occasional grimace or frown, withdrawn, disinterested	Frequent to constant quivering chin, clenched jow
Legs	Normal position or relaxed	Uneasy, restless, tense	Kicking or legs drawn up
Activity	Lying quietly, normal position, moves easily	Squirming, shifting, back and forth, tense	Arched, rigid or jerking
Cry	No cry (awake or asleep)	Moans or whimpers; occasional complaint	Crying steadily, screams, sobs, frequent complaints
Consolability	Content, relaxed	Reassured by touching, hugging or being talked to, distractible	Difficult to console or comfort

 $\underline{https://www1.health.gov.au/internet/publications/publishing.nsf/Content/triageqrg\sim triageqrg-pain\sim triageqrg-FLACC}$

Instructions

Patients who are awake:

- · Observe for at least 2-5 minutes.
- Observe legs and body uncovered.
- · Reposition patient or observe activity; assess body for tenseness and tone.
- · Initiate consoling interventions if needed.

Patients who are asleep:

- · Observe for at least 5 minutes or longer.
- Observe body and legs uncovered.
- · If possible reposition the patient.
- Touch the body and assess for tenseness and tone.

Each category is scored on the 0-2 scale which results in a total score of 0-10.

Assessment of Behavioural Score:

0 = Relaxed and comfortable

1-3 = Mild discomfort

4-6 = Moderate pain

7-10 = Severe discomfort/pain

Reference: Merkel S, Voepel-Lewis T, Shayevitz JR, et al: The GLACC: A behavioural scale for scoring postoperative pain in young children. Pediatric nursing 1997; 23:293-797. Printed with permission © 2002, The Regents of the University of Michigan.
